3.4.5.2 Deaths

The following summaries of deaths will be generated for the safety population.

- Number (%) of patients who died from the first IMP injection until CSED and reasons for death as adjudicated by the CEC;
- Deaths occurring after CSED (adjudicated or not);
- Treatment-emergent adverse events leading to death (death as an outcome on the adverse event case report form page as reported by the Investigator) by primary SOC, HLGT, HLT, and PT sorted by internationally agreed SOC order, with HLGT, HLT, and PT presented in alphabetical order within each SOC;

- All post-treatment adverse events leading to death by primary SOC and PT, sorted by the internationally agreed SOC order and decreasing incidence of PTs within each SOC;
- In addition, deaths in non-randomized patients or randomized but not treated patients will be displayed.

3.4.5.3 Analyses of laboratory variables

Descriptive statistics over time

The summary statistics (including number, mean, median, Q1, Q3 standard deviation, minimum, and maximum) of all laboratory variables (central laboratory values and changes from baseline) will be calculated for each visit or study assessment (baseline, each post-baseline time point, last on-treatment and worst on-treatment value) by treatment group during the treatment period.

For glucose, this summary will be also provided according to the diabetes status at baseline. Only fasting samples will be summarized.

In addition, for some parameters of interest, mean changes from baseline with the corresponding standard error could be plotted over time in each treatment group.

Potentially clinically significant abnormalities

The incidence of PCSAs (list provided in Appendix A) as well as ALT increase as defined as AESI and hemoglobin decrease from baseline ≥ 15 g/L at any time during the TEAE period will be summarized by biological function and treatment group whatever the baseline level and/or according to the following baseline status categories:

- Normal/missing;
- Abnormal according to PCSA criterion or criteria.

For glucose, this summary will also be provided according to the diabetes status at baseline. Only fasting samples will be summarized.

For parameters for which no PCSA criteria are defined, similar table(s) using the normal range will be provided.

PCSA summaries will also be provided in patients from alirocumab group with 2 consecutive LDL-C <25 mg/dL in case a signal detected in the adverse events analyses (see Section 3.4.5.1) warrants further investigations. Only PCSA occurring after the first occurrence of LDL-C <25 mg/dL will be considered (see Section 3.4.5.1, sub-section "Subgroup of patients with two consecutive LDL-C <25 mg/dL (<0.65 mmol/L)" for the definition of the analysis period).

Analysis of new onset of diabetes (NOD)

The incidence of new onset of diabetes during the TEAE period will be analyzed in the subgroup of patients not having diabetes at baseline as well as in the subgroups of patients with pre-diabetes and normal glycemic at baseline (see Section 3.1.1). New onset diabetes will be defined as follows, combining information from adverse events, medication, and laboratory parameters:

- Type 1 or 2 diabetes TEAE (CMQ "Type 1 or type 2 diabetes", Table 11).
- And/or anti-diabetic medication initiated during the TEA E period with a confirmed diagnosis per the external diabetes experts *.

* Patients classified as NOD based only on the use of anti-diabetic medication during the TEAE period will be reviewed in a blinded manner by external experts in diabetology. If the diabetic mellitus status is not confirmed, the patients will not be classified as NOD.

- And/or at least 2 HbA_{1c} \geq 6.5% during the TEAE period
 - For patients with a single measurement available during the TEAE period, a single value $\geq 6.5\%$ will be considered and qualify the patient as NOD by default
 - For patients with several HbA1c measurements but only with the last one $\geq 6.5\%$, this single value $\geq 6.5\%$ will be considered and qualify the patient as NOD by default.
- And/or at least two fasting glucose measurements $\geq 126 \text{ mg/dL}$ (7.0 mmol/L):
 - For patients with only a single measurement available during the TEAE period, a single value ≥126 mg/dL (7.0 mmol/L) will NOT be considered and will NOT qualify the patient as NOD.
 - For patients with several fasting glucose measurements but only with the last one ≥126 mg/dL (7.0 mmol/L), this single value ≥ 126 mg/dL (7.0 mmol/L) will NOT be considered and will NOT qualify the patient as NOD.

Hepatitis C antibody

The number and percentage of patients with a post-baseline seroconversion for hepatitis C test will be provided by treatment group in post-baseline (including the TEAE and post TEAE periods). Post-baseline seroconversion is defined for patients with a negative baseline status who had either a "positive ribonucleic acid" (RNA) or a "confirmed positive antibody with negative RNA" post-baseline status as defined in the table below. Other situations require case by case evaluation and will be described individually if relevant.

The status as regards to hepatitis C virus (HCV) for a patient will be defined as follows for all evaluations (baseline and post-baseline).

	Hepatitis C Antibody (Ab) test result						
	Negative			Positive			
Reflexive test ^a – hepatitis C RNA test	Not available or HCV RNA not detected	HCV RNA detected	HCV RNA not detected ^b	HCV RNA detected	Not available		
Hepatitis C status - label	Negative	Positive RNA	Negative ^b	Positive RNA	Positive Ab – no RNA available		

Table 6 - Definition of the patient status regarding hepatitis C virus

a Test performed at the same time or after the antibody test in the pre-treatment period (for baseline evaluation), or post-baseline, respectively

b For post-baseline evaluation, a second antibody test with a different type of assay is to be done at the same date or after the first antibody test. The result of this test will modify the final hepatitis C status of the patient in some cases (see details in the text below the table)

The baseline evaluation will be based on tests performed during the pre-treatment period.

In case of multiple hepatitis C tests available for the post-baseline evaluation, the positive status of the patient will be defined as follows:

- "Positive RNA" status if at least 1 post-baseline positive RNA is detected, regardless of status of the patient at the end of treatment.
- Else "Positive Ab no RNA available" status if no post-baseline reflexive RNA test is available for at least 1 post-baseline positive antibody test.

If no antibody test is available or with "indeterminate" as result pre-treatment or post-baseline, respectively, the RNA test (if available) will be used alone to determine the status of the patient. If no RNA is available then the hepatitis C status of the patient will be missing.

The post-baseline status "confirmed positive antibody with negative RNA" will replace "Negative" status as defined above in the case where no RNA was detected post-baseline and the 2 antibody tests surrounding the same visit (from 2 different types of assay) are positive.

For a conservative approach, the post-baseline status "Positive Ab - no RNA available" will not be modified by the availability of a second antibody test from a different assay.

Possible drug-induced liver injury

The liver function tests, namely AST, ALT, alkaline phosphatase, and total bilirubin, are used to assess possible drug-induced liver toxicity. The proportion of patients with PCSA values at any post-baseline visit by baseline status will be displayed by treatment group for each parameter.

A graph of distribution of peak values of ALT versus peak values of total bilirubin will also be presented. Note that the ALT and total bilirubin values are presented on a logarithmic scale. The graph will be divided into 4 quadrants with a vertical line corresponding to 3 x ULN for ALT and a horizontal line corresponding to 2 x ULN for total bilirubin.

Graph and listing of possible Hy's law cases identified by treatment group (eg, patients with any elevated ALT>3 x ULN, and associated with an increase in bilirubin ≥ 2 x ULN) with ALT, AST, alkaline phosphatase, total bilirubin, and, if available, direct and indirect bilirubin, will be provided.

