- In the TNT trial, patients in the lowest quartile of achieved LDL-C had value <64 mg/dL and a mean LDL-C level of 54 mg/dL as compared to means of 70, 83, 97 and 122 mg/dL in the remaining quintiles. Within these quintiles, there was a strong and significant relationship between the lower achieved LDL-C levels and lower rates of major CV events ( $p < 0.0001$ ) (13).

- In the JUPITER trial, the investigators split the patients in the rosuvastatin group into two cohorts of achieved LDL-C <50 mg/dL (n=4154) and >50 mg/dL (n=4000) and compared them to the placebo group. Those that had achieved LDL-C <50 mg/dL demonstrated significantly lower rates of CV events than either of the other two groups (14).

In none of these three analyses there was evidence of an adverse safety signal observed with patients that achieved these lower levels of LDL-C. A recent communication compared patients who achieved a LDL-C  $\leq$ 30 mg/dL (n=621) versus those with LDL-C >30 mg/dL (n=7533) (15). No differences in overall TEAEs and many other specific AEs were observed, with the exception of a greater incidence in insomnia (1.6/100 PY versus 1.2/100 PY; p=0.031) and hematuria (1.8 /100 PY versus 1.1/100 PY; p=0.0007) among patients with LDL-C  $\leq$ 30 mg/dL. The rate of clinically relevant declines in eGFR ( $\geq$ 30%) tended to be lower among patients with lower reduction in LDL-C.

Similar findings have been observed in a patient-level meta-analysis conducted by the Cholesterol Trialists Treatment Collaboration. This examination of 26 large statin CV event trials encompassing approximately 170,000 patients has demonstrated that 20% reduction in major CV events can be derived for every 1 mmol/L (38.6 mg/dl) reduction in LDL-C, even in patients whose starting LDL-C levels are less than 2 mmol/L (77 mg/dl) (16). This meta-analysis has also demonstrated no significant safety risks with long-term cholesterol reduction treatment, including cancer (17).

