### Urine samplings:

- Urinalysis will be performed periodically (yearly) throughout the study in about 750 randomized patients, at selected sites. A urine sample will be sent to Covance Central Labs for macroscopic analysis (presence of blood, protein, glucose, ketones, nitrates, leukocyte esterase, uro-bilinogen and bilirubin). In case of abnormalities, Covance Central Lab will perform a microscopic analysis.
- Urine pregnancy test – dipstick will be performed on site.

**NOTE:** Any clinically relevant abnormal laboratory value should be immediately rechecked (whenever possible using the central laboratory) for confirmation before making any decision for the concerned patient. It should be documented as an AE/SAE as applicable. Please also refer to [Section 10.4.4](#) and [Section 10.4.7](#).

Decision trees for the management of certain laboratory abnormalities by Sanofi are provided in [Appendix C](#) and [Appendix D](#)

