#### 10.4.4 General guidelines for reporting adverse events

- AEs are to be recorded in corresponding screen(s) included in the eCRF.
- The reporting requirement of AEs depends on patient status (study completer or patient who had premature permanent discontinuation of IMP)
  - In patients who receive IMP until the end of the study (study completer), all AEs, regardless of seriousness or relationship to IMP/NIMP, spanning from the signature of the informed consent form until the CSED visit are to be recorded in the eCRF. Patients who experience a new or ongoing related or serious AE or a new or ongoing AESI (see [Section 10.4.2](#)) at the CSED visit should be followed beyond the CSED visit until resolution, stabilization, or death (whichever comes first) and related data will be collected (see [Section 10.1.5.4.1](#)).
  - In patients who have permanent premature IMP discontinuation:
    - All AEs, regardless of seriousness or relationship to IMP/NIMP, spanning from the signature of the informed consent form until 6 months following V70 (end of treatment visit) are to be recorded in the eCRF.
    - From 6 months following V70 until the CSED visit, related and/or serious AEs should be recorded in the eCRF.

***NOTE:** Reporting requirement for suspected efficacy endpoints is the same regardless of patient status (study completers or patients who had premature permanent discontinuation of IMP); suspected efficacy endpoints should be reported in all randomized patients until the end of the study (CSED).*

- Whenever possible, diagnosis or single syndrome should be reported instead of symptoms. The Investigator should specify the date of onset, intensity, action taken with respect to IMP, corrective treatment/therapy given, additional investigations performed, outcome, and his/her opinion as to whether there is a reasonable possibility that the AE was caused by the IMP.
- When treatment is prematurely discontinued, the patient will be maintained in the study and the patient's observations will continue until the common study end date visit (see [Section 10.3.4](#)).
- Laboratory, vital signs or ECG abnormalities are to be recorded as AEs only if:
  - Symptomatic and/or
  - Requiring either corrective treatment or consultation, and/or
  - Leading to IMP discontinuation or modification of dosing (with exception of LDL-C levels which may lead to IMP dosing modification, but in a blinded manner), and/or

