#### 10.4.6 Guidelines for reporting adverse events of special interest

##### 10.4.6.1 Reporting of adverse events of special interest with immediate notification

For these AEs, the Sponsor will be informed immediately (ie within 24 hours), as per SAEs notification described in [Section 10.4.5](#), even if not fulfilling a seriousness criterion, using the corresponding screens in the eCRF.

- ALT  $\geq 3$  ULN (if baseline ALT < ULN) Or ALT  $\geq 2$  times the baseline value (if baseline ALT  $\geq$  ULN) (Please refer to related flowchart in [Appendix C](#)).
- Allergic events
  - Allergic drug reactions and/or local injection site reactions deemed to be allergic (or have an allergic component) that require consultation with another physician for further evaluation of hypersensitivity/allergy, as per the investigator's medical judgment or as per [Section 10.6.2](#), should be reported as an AESI with immediate notification.
  - All allergic events, and all injection site reactions having an allergic component or deemed to be allergic, require completion of the specific eCRF screen (see [Section 10.6.2](#)), regardless of requirements for immediate reporting.

- Hemolytic anemia (see [Section 10.4.7.1](#) and [Appendix D](#))
  - If there is a decrease in hemoglobin and reflexive testing as per [Appendix D](#) suggesting hemolysis, then report this as an AESI with immediate notification. Special eCRF screen will need to be completed
- Pregnancy
  - *Pregnancy occurring in a female patient enrolled in the study* will be recorded as a pre-specified AE with immediate notification in all cases, and IMP should be discontinued in all cases. It will be qualified as an SAE only if it fulfills the SAE criteria. The follow-up of the pregnancy will be mandatory until the outcome of the pregnancy has been determined.
  - *Pregnancy occurring in the female partner of a male patient included in the clinical trial*: if permitted by the female partner and by local regulatory policies, it will be recorded as a pre-specified AE with immediate notification (SAE if it fulfills the SAE criteria), and pregnancy should be followed-up until the outcome has been determined.
- Symptomatic Overdose with IMP

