#### 10.4.7 Guidelines for management of specific laboratory abnormalities

Laboratory abnormalities with pre-specified monitoring should be monitored, documented, and managed according to the related flowchart in protocol [Appendix C](#) and [Appendix D](#)

- Neutropenia
- Thrombocytopenia
- Increase in ALT
- Acute renal insufficiency
- Decrease in hemoglobin (defined as  $\geq 1.5$  g/dL decrease from pre-randomization baseline value)
- Increase in CPK (other than cardiac-related) and suspicion of rhabdomyolysis.

Investigators are strongly encouraged to follow these algorithms in [Appendix C](#) and [Appendix D](#), especially in situations where the abnormality persists or when there is no clear explanation for the observed abnormality.

However there may be situations where these algorithms are not entirely applicable, therefore Investigator may use his/her best judgment. Also, in some situations, the Sponsor may wish to discuss with the Investigator. Examples where these algorithms may not be applicable include (but are not limited to) the following situations:

- patients with known stable low or borderline neutrophil or platelet count or impaired renal function at baseline; Investigator should attempt to have a diagnosis for the observed finding and should use his/her best judgment whether or not to enroll these patients, and if

patient is enrolled, on how to best monitor these baseline abnormalities throughout the study

- patients with ALT increase or elevated CK for which the abnormality resolves following statin dose reduction or statin discontinuation
- patients with elevated CK caused by a myocardial infarction

In addition, discontinuation caused by a laboratory abnormality can be either permanent or temporary, depending on the particular case. There is no requirement for permanent treatment discontinuation in every case of the general guidance for the follow up of selected laboratory abnormalities mentioned in [Appendix C](#).

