#### **10.4.7.1 Hemoglobin decrease**

See [Appendix D](#).

At the first post-randomization study visit with occurrence of a hemoglobin (Hb) measurement decrease by  $\geq 1.5$  g/dL as compared to the randomization visit hemoglobin measurement, then the Central Lab will reflexively measure haptoglobin using specimens already obtained at the same time point for which the hemoglobin decrease was detected. The Central Lab will then provide the results of the reticulocyte count, haptoglobin, LDH and indirect bilirubin (reflexively measured only if the total bilirubin  $>$  ULN) to the Investigator.

***NOTE:** At selected sites with a longer transit time to Central Lab where reticulocyte count cannot be measured by Central Lab, a second hematology sample will be collected for local assessment of reticulocyte count,*

- If the following pattern of abnormalities is noted:
  - Reticulocyte count  $>$  Central Lab (or if applicable, local lab) upper limit of the reference range (also referred to as ULN) **AND**
  - Haptoglobin  $<$  Central Lab's lower limit of the reference range (also referred to as LLN) **AND**
  - LDH  $>$  ULN **AND**
  - Indirect bilirubin  $>$  ULN (only if the total bilirubin  $>$  ULN)

The patient should be referred to a hematologist. The hematologist should obtain a peripheral blood smear and anti-erythrocyte antibodies (direct and indirect) by Coombs test. Further investigations are at the discretion of the hematologist.

- If the results are normal or the pattern of abnormality is something other than that described above, then the Investigator should exercise his/her medical judgment in the interpretation of the results, necessity for workup of the decrease in hemoglobin or referral to a hematologist

If a second hemoglobin measurement demonstrating a further decrease of  $\geq 1$  g/dL from the last available value is observed, even if the previous work-up was negative, the same investigations can be repeated and a hematology consultation can be requested at the discretion of the Investigator or at the Sponsor's request.

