#### **LDL-C <25 mg/dL:**

Summaries of adverse events will be also provided on the safety subgroup population of patients with two consecutive LDL-C <25mg/dL in the alirocumab group. Only adverse events, for which it will be confirmed or unclear that they occurred, worsened or became serious after the first level of LDL-C <25mg/dL will be considered.

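### Apart from glycemic changes and the ALT and hemolytic anemia AESIs, laboratory abnormalities not recorded as AEs cannot themselves trigger the PCSA table for patients with two LDL-C values below 25 mg/dL

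*SAP*

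**What the plan says.** SAP 3.4.5.3 always tabulates PCSAs, the ALT increase defined as an AESI, and hemoglobin falls of at least 15 g/L. The tables are by treatment group, overall and/or by baseline status. For alirocumab patients with two consecutive low values the same section is conditional: PCSA summaries are given for "LDL-C <25 mg/dL in case a signal detected in the adverse events analyses" of SAP 3.4.5.1 calls for further investigation.

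The analyses in SAP 3.4.5.1 that supply the signal screen TEAEs at every MedDRA level plus four groupings: cataract, neurologic events, neurocognitive disorders and new onset of diabetes. They are run by achieved LDL-C and by baseline LDL-C category, at thresholds of 25 and 15 mg/dL. No numerical definition of a signal is given.

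What can enter that screen depends on protocol 10.4.4: "Laboratory, vital signs or ECG abnormalities are to be recorded as AEs only if" they are symptomatic, need treatment or consultation, change dosing, are clinically relevant, are serious, or are AESIs with immediate notification.

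For this subgroup, protocol 11.4.3.1 planned adverse events only: "Summaries of adverse events will be also provided on the safety subgroup population" with two low values. The SAP adds the laboratory table but makes it depend on the adverse-event result.

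**The concern.** A PCSA table is meant to show laboratory values that matter whether or not an investigator reported them as events. Requiring an adverse-event signal first means that the laboratory data cannot speak for themselves in the one subgroup where the question is open. Protocol 10.6.3 says that the lower limit of safe LDL-C lowering has not been established, and protocol Section 4 stresses how few patients with very low LDL-C have been studied.

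If an effect were confined to very low LDL-C and stayed below the AE criteria, the final analysis would show it only after averaging over all other alirocumab patients. The adverse-event comparison by achieved LDL-C is unconditional; only its laboratory counterpart is gated. No efficacy result, type I error or randomized safety comparison is at stake.

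**Working it through.** **1. Which laboratory changes can reach the trigger**

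- *Glycemic changes: yes.* SAP 3.4.5.3 lets new onset of diabetes be met on two HbA1c values of at least 6.5% (one in some cases) or two fasting glucose values of at least 126 mg/dL, with no AE. SAP 3.4.5.1 analyses it by low LDL-C in both steps, signal or not.
- *ALT rises and hemolytic anemia: yes.* Both are immediate-notification AESIs in protocol 10.4.6.1. A hemoglobin fall with reflex tests "suggesting hemolysis, then report this as an AESI with immediate notification".
- *Values judged clinically relevant: yes.* This is a criterion in 10.4.4, and the note in protocol Section 10 adds: "Any clinically relevant abnormal laboratory value should be immediately rechecked" and documented as an AE where applicable.
- *Neutropenia, thrombocytopenia, renal insufficiency, hemoglobin and CPK: partly.* Protocol 10.4.7 has algorithms, but "Investigators are strongly encouraged to follow these algorithms" and may use judgment instead.
- *Everything else below the AE criteria: no.*

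Hemoglobin is the clearest internal example. The SAP tabulates a fall of at least 15 g/L by arm. Protocol 10.4.7.1 acts on the same fall (1.5 g/dL), but without the full hemolysis pattern "the Investigator should exercise his/her medical judgment in the interpretation of the results, necessity for workup of the decrease in hemoglobin" or referral. Such a fall may never become an AE.

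**2. Scheduled samples in the low-LDL-C window (down-titrated patients)**

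Inputs are the visits in protocol 1.2.1 and the SAP 3.4.5.1 rule that the window ends 70 days after the last 150 mg injection. The first low value is at visit *i*, the second at *i*+1 and the down-titration at *i*+2. The last 150 mg injection is 0 to 14 days before visit *i*+2. Samples are counted strictly after the first low value.

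| First low value | Down-titration | Window ends | Hematology/chemistry | CPK/liver |
|---|---|---|---|---|
| M4 | M12 | M13.8–14.3 | 1 (M12) | 1 (M12) |
| M12 | M20 | M21.8–22.3 | 0 | 2 (M16, M20) |
| M24 | M36 | M37.8–38.3 | 1 (M36) | 2 (M30, M36) |

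Over all starts from M4 to M48, hematology/chemistry gives 1, except 0 at M12. CPK/liver gives 2, except 1 at M4.

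For comparison, take protocol Table 3 accrual with treatment to M64: 2004 patients by M11 and the remaining 15,996 spread evenly over M12–M40. Mean follow-up is then 40.4 months, with 3.8 hematology/chemistry and 9.1 CPK/liver samples. Crude percentages from the two periods are therefore not comparable. Unscheduled and repeat values also count under SAP 3.4.5. Patients who stay on 75 mg are followed to the end of the TEAE period.

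**3. Dilution, on assumed rates**

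The documents give no PCSA rates. Assume 1% risk per sample, 3 samples, and 1.5% while LDL-C is very low.

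- Placebo: 1 − 0.99³ = 0.0297.
- Excess throughout: 1 − 0.985³ = 0.0443 (ratio 1.49).
- Excess for one sample: 1 − 0.985 × 0.99² = 0.0346 (ratio 1.16).

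With share *f* of alirocumab patients affected, the by-arm risk is *f* × (raised risk) + (1 − *f*) × 0.0297. Power uses the two-proportion normal approximation with unpooled variance, two-sided 0.05 and 9300 per arm.

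| *f* | Ratio, one sample | Power | Ratio, throughout | Power |
|---|---|---|---|---|
| 2% | 1.003 | 5% | 1.010 | 5% |
| 5% | 1.008 | 5% | 1.025 | 6% |
| 10% | 1.016 | 5% | 1.049 | 9% |
| 20% | 1.033 | 7% | 1.098 | 21% |
| 40% | 1.066 | 12% | 1.197 | 61% |

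The result depends on the inputs. With 9 samples and the excess throughout, power at shares of 20% and 40% is 49% and 97%. With 3 samples and the risk doubled to 2%, it is 61% and 99%.

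**The case against.** The strongest reply is that little is left in the gap. Non-lipid central results go to the sites, clinical relevance is itself an AE criterion, and the main organ systems have algorithms or AESI rules. What remains is largely what an informed investigator judged unimportant. That narrows the gap but does not close it, since the algorithms allow judgment.

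The gate is also soft. With no numerical definition of a signal, a muscle, renal or anemia TEAE could open the table. This stands, and it is why the point is limited to laboratory changes acting as their own trigger. It also leaves the decision to judgment after results are seen.

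Protocol 6.4 and 10.6.3 provide review of these patients by the CV DMC and an independent physician. That is real protection during the trial, but it is not a final-analysis output.

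The eGFR remark in protocol Section 4 is weak support. It concerns a statin comparison, and its direction (declines "tended to be lower among patients with lower reduction in LDL-C") is unclear.

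A reader might infer that no laboratory change without an AE can open the table, or that all are shown only by arm. New onset of diabetes refutes both. A reader might also take 61% as the most power the by-arm table could have; the reruns at 97% and 99% show that it is not.

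**Conclusion.** The point holds in its limited form. Outside the glycemic criteria and the ALT and hemolytic anemia AESIs, a laboratory abnormality not recorded as an AE cannot itself trigger the low-LDL-C PCSA table. Unless another TEAE signal does, no planned final output shows it by achieved LDL-C.

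The number of PCSAs affected cannot be determined: the documents give no PCSA rates, and the appendices holding the algorithms are not in the available text. The sample counts follow from the visit schedule. The dilution and power figures rest on assumed risks, sample numbers and shares. They show the direction only: low power at small shares or with a short-lived excess, but not necessarily at large shares with a lasting one. Protocol Section 4 anticipates few patients below 25 mg/dL under this titration scheme, which makes the small shares likelier. Severity is minor.

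**What to change.** In SAP 3.4.5.3, delete the clause that makes the low-LDL-C PCSA summaries depend on a signal in the 3.4.5.1 adverse-event analyses. Always report PCSAs, hemoglobin decrease of at least 15 g/L and the ALT AESI criterion descriptively, for alirocumab patients with versus without two consecutive LDL-C values below 25 mg/dL, and again at 15 mg/dL. Use rates per 100 patient-years on the 3.4.5.1 analysis periods, show the number of patients sampled for each parameter, and repeat the SAP's own caveat that these groups are formed after randomization.

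Optionally, add alirocumab versus placebo by baseline LDL-C category, as in the second screening approach, for description only. It keeps the randomized comparison but is weak. On the assumed rates, a category holding 30% of patients (0.30 × 9300 = 2790 per arm), of whom 40% reach two low values, gives 7% power (excess for one sample) to 23% (throughout).

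The cost is SAP wording and a few tables from data already collected. Some chance differences will need medical judgment. Down-titrated patients will contribute few scheduled samples: 0 to 1 for hematology/chemistry and 1 to 2 for CPK/liver.

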### 7.2.1 Exclusion criteria related to study methodology

- E 01. Age < 40 years.
- E 02. (A6) Uncontrolled hypertension (multiple readings with SBP > 180 mmHg or DBP > 110 mmHg) at V3.
- E 03. History of New York Heart Association (NYHA) class III or IV congestive heart failure persisting despite treatment or, if measured, LVEF < 25% at the most recent measurement.
- E 04. Known history of hemorrhagic stroke.
- E 05. History of cancer within the past 5 years, except for adequately treated basal cell skin cancer, squamous cell skin cancer, or in situ cervical cancer.
- E 06. (A6) Recent diagnosis of hypothyroidism for which treatment was initiated within 1 month prior to qualifying visit (V2).
- E 07. Patient who has been previously treated with at least one dose of alirocumab or any other anti-PCSK9 monoclonal antibody in other clinical trials.
- E 08. Patient who has taken other investigational drugs within 1 month or 5 half-lives, whichever is longer.
- E 09. (A6) Laboratory findings measured during screening and before randomization visit:
- Positive test for hepatitis B surface antigen
  - Positive hepatitis C antibody confirmed with positive RNA testing ( indicative of active hepatitis C infection)

- Triglycerides (TG) > 400mg/dL (>4.52 mmol/L) (1 repeat lab allowed)
- Positive serum or urine pregnancy test in females of childbearing potential
- eGFR <30 mL/min/1.73 m^2 according to 4-variable MDRD Study equation (calculated by central lab)
- ALT or AST >3 x ULN on most recent determination prior to randomization (1 repeat lab is allowed)
- CPK >3 x ULN on most recent determination prior to randomization (1 repeat lab is allowed)

E 10. Conditions/situations such as:

- Any clinically significant abnormality identified at the time of screening that in the judgment of the Investigator or any sub-Investigator would preclude safe completion of the study or constrain endpoints assessment such as major systemic diseases, patients with short life expectancy.
- Patients considered by the Investigator or any sub-Investigator as inappropriate for this study for any reason, eg:
  - Those deemed unable to meet specific protocol requirements, such as scheduled visits
  - Investigator or any sub-Investigator, pharmacist, study coordinator, other study staff or relative thereof directly involved in the conduct of the protocol, etc

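### Hepatitis C antibody-positive, RNA-negative patients are classed as negative at baseline and can later be counted as new seroconversions

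*SAP*

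**What the plan says.** Protocol 11.4.3.2 plans a count and percentage of hepatitis C seroconversions by treatment group and does not define the term. The definition is in SAP 3.4.5.3: "Post-baseline seroconversion is defined for patients with a negative baseline status who had either a" status of positive RNA or of confirmed positive antibody without RNA.

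Table 6 of the SAP sets the labels for baseline and post-baseline evaluations alike. Under a positive antibody test, the column "HCV RNA not detected ^b" carries the label *Negative*. Footnote b and the text below the table allow a second antibody test, by a different type of assay, to change that label at post-baseline evaluations only. The confirmed-antibody status replaces *Negative* "in the case where no RNA was detected post-baseline and the 2 antibody tests surrounding the same visit" are both positive. For baseline the SAP says only this: "The baseline evaluation will be based on tests performed during the pre-treatment period".

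On eligibility, Protocol 7.2.1 (E09) excludes "Positive hepatitis C antibody confirmed with positive RNA testing". A positive antibody without detectable RNA does not exclude a patient.

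**The concern.** Seroconversion ordinarily means that a patient without antibody acquires it. The SAP's at-risk group is defined by a label that also covers patients who already have antibody. Because the second assay is used only after baseline, one serological state has two names, depending on when it is seen. Crossing from one name to the other is counted as an event.

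What is at stake is the accuracy of one planned safety table. Cases that predate the first dose would be added to on-study cases and could not be told apart in the reported count.

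**Working it through.** The plan has no figure to reproduce here, so the check traces patients through the rules.

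**Step 1, entry.** E09 admits patients with positive antibody and undetected RNA. The protocol asks for a confirmatory sample after a positive antibody test, so a patient positive at V1 would normally have an RNA result before randomization.

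**Step 2, retest.** The flow chart (Protocol 1.2.1) schedules the antibody test at V1, V3, V30 for completers, and V70. The reduced V30 list for prematurely discontinued patients (Protocol 10.1.5.4.2) omits it.

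**Step 3, labels.** Applying Table 6, footnote b and the seroconversion definition gives:

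| Baseline antibody / RNA | Baseline label | Post-baseline antibody / RNA / second assay | Post-baseline label | Counted? |
|---|---|---|---|---|
| negative / none | Negative | positive / not detected / positive | confirmed antibody | yes, correctly |
| positive / not detected | Negative | positive / not detected / positive | confirmed antibody | **yes, although antibody was already present** |
| positive / not detected | Negative | positive / not detected / negative or not done | Negative | no |
| positive / not detected | Negative | positive / detected | Positive RNA | yes, although antibody was already present |
| negative / detected | Positive RNA | any | any | no |

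The second row is the problem. The first and second rows fall into the same count. The SAP's clause on case-by-case evaluation covers situations outside the definition; the second row meets the definition, so the clause does not remove it.

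**Step 4, size.** From the documents: about 9,300 patients per arm (Protocol 11.1). Assumed, because the documents are silent: prevalence p of positive antibody with undetected RNA at entry, 0.1% to 2%; share c of these who are retested and positive on both assays, 50% to 90%.

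Spurious cases per arm = 9,300 × p × c

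- Low: 9,300 × 0.001 × 0.5 = 4.65, about 5
- Middle: 9,300 × 0.005 × 0.9 = 41.85, about 42
- High: 9,300 × 0.02 × 0.9 = 167.4, about 167

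As a share of the arm this is p × c, from 0.05% to 1.8%.

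**Step 5, effect on a comparison.** Take an invented true split of 15 against 5 (ratio 3.0, difference 10) and add equal spurious cases to each arm:

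- 4.65 per arm: 19.65 / 9.65 = 2.04
- 41.85 per arm: 56.85 / 46.85 = 1.21
- 167.4 per arm: 182.4 / 172.4 = 1.06

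The difference stays at 10 throughout. Only the ratio shrinks.

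**The case against.** The strongest reply is that little depends on this. The output is a descriptive count and percentage. No ratio is planned for it, and Protocol 11.4.3 rules out formal inferential testing of safety data. Randomization should spread pre-existing infections about evenly, so the between-arm difference is largely preserved. All of that stands, and it limits the importance of the point. It does not make the count right.

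Three stronger readings are tempting, and the documents do not support them.

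- A reader might infer that merely repeating the baseline result counts as seroconversion. It does not: with one positive assay and undetected RNA the label stays *Negative*. A second, different assay must also be positive. That step screens out false-positive antibody results, but it cannot tell an old infection from a new one.
- A reader might infer that the rule also loses true cases, because an antibody-positive patient with no RNA result is outside the definition. Such patients fall under the case-by-case clause, and the protocol calls for a confirmatory sample after any positive antibody test. The sentence beginning "For a conservative approach, the post-baseline status" means that a second assay cannot clear a patient already labelled positive, which is a cautious choice for safety.
- A reader might infer that the table would chiefly measure past infection. That depends on the prevalence of past infection and the incidence of new infection, and the documents give neither.

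**Conclusion.** The definition is internally inconsistent and, for the path shown, gives a wrong count. A patient with antibody before the first dose can be reported as an on-study seroconversion. The direction is clear: counts and percentages rise in both arms and relative differences shrink. Neither arm is favoured, and no efficacy analysis is affected.

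The size is uncertain. The range of about 5 to 167 spurious cases per arm rests wholly on the assumed prevalence and retest shares. It also assumes that the run-in RNA result is paired with the baseline antibody test; the SAP does not say how V1 and V3 antibody results are to be combined. The inconsistency itself rests on the text alone. This is a small point, worth correcting because correction is cheap.

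**What to change.** In SAP 3.4.5.3, for the seroconversion analysis only:

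1. Keep the Table 6 baseline status *Negative* as a condition, and add that no pre-treatment antibody test (V1 or V3) was positive. Both conditions are needed. Antibody negativity alone would admit the antibody-negative, RNA-detected patient whom Table 6 now correctly keeps out.
2. Leave the existing handling of RNA-detected, indeterminate and missing baseline results unchanged.
3. Show patients with positive antibody and undetected RNA at baseline in a separate row, outside numerator and denominator. Describe any new RNA detection in them individually.

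While editing, note that the definition refers to Table 6 for the confirmed-antibody status, which appears only in the text below the table.

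The cost is a few sentences and a small programming change before database lock. The data are already collected.
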